8.2.2 Methods for Evaluation of Measurable Disease

All measurements should be taken and recorded in metric notation using a ruler or calipers. All baseline evaluations should be performed as closely as possible to the beginning of treatment and

never more than 28 days before the beginning of the treatment. Tumor response will be assessed per RECIST 1.1 using radiographic scans every 8 weeks±7 days.

The same method of assessment and the same technique should be used to characterize each identified and reported lesion at baseline and during follow-up. Imaging-based evaluation is preferred to evaluation by clinical examination unless the lesion(s) being followed cannot be imaged but are assessable by clinical exam.

Clinical lesions: Clinical lesions will only be considered measurable when they are superficial

calipers (e.g., skin nodules). In the case of skin lesions, documentation by color photography, including a ruler to estimate the size of the lesion, is recommended.

Chest x-ray: Lesions on chest x-ray are acceptable as measurable lesions when they are clearly defined and surrounded by aerated lung. However, CT is preferable.

Conventional CT and MRI: This guideline has defined measurability of lesions on CT scan based on the assumption that CT slice thickness is 5 mm (0.5 cm) or less. If CT scans have slice thickness greater than 5 mm (0.5 cm), the minimum size for a measurable lesion should be twice the slice thickness. MRI is also acceptable in certain situations (e.g., for body scans).

MRI has excellent contrast, spatial, and temporal resolution; however, there are many image acquisition variables involved in MRI, which greatly impact image quality, lesion conspicuity, and measurement. As with CT, if an MRI is performed, the technical specifications of the scanning sequences used should be optimized for the evaluation of the type and site of disease. Furthermore, as with CT, the modality used at follow-up should be the same as was used at baseline and the lesions should be measured/assessed on the same pulse sequence.

PET-CT: At present, the low dose or attenuation correction CT portion of a combined PET-CT is not always of optimal diagnostic CT quality for use with RECIST measurements. However, if the site can document that the CT performed as part of a PET-CT is of identical diagnostic quality to a diagnostic CT (with IV and oral contrast), then the CT portion of the PET-CT can be used for RECIST measurements and can be used interchangeably with conventional CT in accurately measuring cancer lesions over time. Note, however, that the PET portion of the CT introduces

additional data which may bias an investigator if it is not routinely or serially performed. Further, if the subject is allergic to contrast dye, the case should be discussed with the IND Sponsor.

Ultrasound: Ultrasound is not useful in assessment of lesion size and should not be used as a method of measurement. If new lesions are identified by ultrasound in the course of the study, confirmation by CT or MRI is advised. If there is concern about radiation exposure at CT, MRI may be used instead of CT in selected instances.

Endoscopy, Laparoscopy: The utilization of these techniques for objective tumor evaluation is not advised.

Tumor markers (CA 19-9): Tumor markers alone cannot be used to assess response. If markers are initially above the upper normal limit, they must normalize for a subject to be considered in complete clinical response.

Cytology: The cytological confirmation of the neoplastic origin of any effusion that appears or worsens during treatment when the measurable tumor has met criteria for response or stable disease is mandatory to differentiate between response or stable disease (an effusion may be a side effect of the treatment) and progressive disease.

FDG-PET: While FDG-PET response assessments need additional study, it is sometimes reasonable to incorporate the use of FDG-PET scanning to complement CT scanning in assessment of progression (particularly possible 'new' disease). New lesions on the basis of FDG-PET imaging can be identified according to the following algorithm:

- Negative FDG-PET at baseline, with a positive FDG-PET at follow-up is a sign of PD based on a new lesion.
- No FDG-PET at baseline and a positive FDG-PET at follow-up: If the positive FDG-PET at follow-up corresponds to a new site of disease confirmed by CT, this is PD. If the positive FDG-PET at follow-up is not confirmed as a new site of disease on CT, additional follow-up CT scans are needed to determine if there is truly progression occurring at that site (if so, the date of PD will be the date of the initial abnormal FDG-PET scan). If the positive FDG-PET at follow-up corresponds to a pre-existing site of disease on CT that is not progressing on the basis of the anatomic images, this is not PD.

• FDG-PET may be used to upgrade a response to a CR in a manner similar to a biopsy in cases where a residual radiographic abnormality is thought to represent fibrosis or scarring. The use of FDG-PET in this circumstance should be prospectively described in the protocol and supported by disease-specific medical literature for the indication. However, it must be acknowledged that both approaches may lead to false positive CR due to limitations of FDGPET and biopsy resolution/sensitivity.

NOTE: A 'positive' FDG-PET scan lesion means one which is FDG avid with an uptake greater than twice that of the surrounding tissue on the attenuation corrected image.

8.3 Response Criteria

8.3.1 Evaluation of Target Lesions

Complete Response (CR): Disappearance of all target lesions determined by two separate observations conducted not less than 4 weeks apart. Any pathological lymph nodes (whether target or non-target) must have reduction in short axis to <10 mm (<1 cm). There can be no appearance of new lesions.

Partial Response (PR): At least a 30% decrease in the sum of the diameters of target lesions, taking as reference the baseline sum diameters.

Progressive Disease (PD): At least a 20% increase in the sum of the diameters of target lesions, taking as reference the smallest sum on study (this includes the baseline sum if that is the smallest on study). In addition to the relative increase of 20%, the sum must also demonstrate an absolute increase of at least 5 mm (0.5 cm). (**NOTE:** the appearance of one or more new lesions is also considered progressions).

Stable Disease (SD): Neither sufficient shrinkage to qualify for PR nor sufficient increase to qualify for PD, taking as reference the smallest sum diameters while on study.

8.3.2 Evaluation of Non-Target Lesions

Complete Response (CR): Disappearance of all non-target lesions and normalization of tumor marker level. All lymph nodes must be non-pathological in size (<10 mm [<1 cm] short axis). **NOTE**: If tumor markers are initially above the upper normal limit, they must normalize for a subject to be considered in complete clinical response.

Non-CR/Non-PD: Persistence of one or more non-target lesion(s) and/or maintenance of tumor marker level above the normal limits.

Progressive Disease (PD): Appearance of one or more new lesions and/or unequivocal progression of existing non-target lesions. Unequivocal progression should not normally trump target lesion status. It must be representative of overall disease status change, not a single lesion increase.

Although a clear progression of "non-target" lesions only is exceptional, the opinion of the treating physician should prevail in such circumstances, and the progression status should be confirmed at a later time by the review panel (or PI).

8.3.3 Evaluation of Best Overall Response

The best overall response is the best response recorded from the start of the treatment until disease progression/recurrence (taking as reference for progressive disease the smallest measurements recorded since the treatment started).

The subject's best response assignment will depend on the achievement of both measurement and confirmation criteria (*Table 8.3.1*).

Target	Non-Target	New	Overall	Best Overall Response when
Lesions	Lesions	Lesions	Response	Confirmation is Required ¹
CR	CR	No	CR	

Table 8.3.1 For Subjects with Measurable Disease (e.g., Target Disease)

CR	Non-CR/Non-PD	No	PR	
CR	Not evaluated	No	PR	>4 wks confirmation
PR	Non-CR/Non- PD/not evaluated	No	PR	
SD	Non-CR/Non- PD/not evaluated	No	SD	Documented at least once >4 wks. from baseline
PD	Any	Yes or No	PD*	
Any	PD**	Yes or No	PD*	no prior SD, PR or CR
Any	Any	Yes	PD	

*A minority of subjects treated with immunotherapy may derive clinical benefit either delayed responses, stable disease, or increased overall survival despite initial evidence PD with nivolumab or combination treatment.

Subjects may be permitted to continue treatment beyond initial RECIST 1.1-defined PD (see **Section 4.9**). In these cases, a radiological assessment will be repeated 4 weeks later to confirm or not the progression disease, as defined by RECIST criteria.

** In exceptional circumstances, unequivocal progression in non-target lesions may be accepted as disease progression.

NOTE: Subjects with a global deterioration of health status requiring discontinuation of treatment without objective evidence of disease progression at that time should be reported as "symptomatic deterioration;" (e.g., weight loss >10% of baseline body weight; worsening of tumor-related symptoms, decline in performance status >1 left on ECOG scale) after discussion with IND Sponsor. Every effort should be made to document the objective progression even after discontinuation of Treatment.

8.3.4 Confirmation of Response

Confirmation of response is required per RECIST 1.1.

8.3.5 Duration of Response

Duration of overall response: The duration of overall response is measured from the time measurement criteria are met for CR or PR (whichever is first recorded) until the first date that recurrent or progressive disease is objectively documented (taking as reference for progressive disease the smallest measurements recorded since the treatment started) or death. Subjects who remain alive and have not progressed or received new therapy will be censored on the date of last protocol specified tumor assessment. Subjects who receive new therapy will be censored at the start of the therapy.

Duration of stable disease: The duration of stable disease is measured from the start of the treatment until the first date that recurrent or progressive disease is objectively documented (taking as reference the smallest measurements recorded since the treatment started, including the baseline measurements) or death. Subjects who remain alive and have not progressed or received new therapy will be censored on the date of last protocol specified tumor assessment. Subjects who receive new therapy will be censored at the start of the therapy.

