8.3.6 Progression-Free Survival

Progression-free survival (PFS) is defined as the duration of time from start of treatment to time of progression per RECIST1.1 or death whichever comes first. PFS for patients who are not progressed at the time of data analysis will be censored on the date of the latest tumor assessment. Patients who go off treatment and begin alternate therapy, prior to progressing on this protocol will be censored at the time on the date of the latest tumor assessment before starting the alternate therapy. We assume that all patients have radiographic scans during screening period and before starting treatment. The following table describes how PFS event is defined and PFS time is calculated. Only radiographic scans used to tumor assessment per RECIST 1.1 before starting the alternate therapy will be counted if patients go off treatment and begin alternate therapy. The following table shows how PFS is defined in various scenarios (*Table 8.3.2*).

Scenario	PFS event (1) or censor (0)	PFS time
At least one post treatment scan is available and tumor response is evaluated according to RECIST 1.1 and all scans are completed on the schedule or off the schedule within a month and patient is alive at the latest follow-up.	1 if PD 0 if no PD	The date of the latest tumor assessment – the date of starting treatment

Table 8.3.2 Definition of PFS

At least one post treatment scan is available and tumor response is evaluated according to RECIST 1.1, but the gap between radiographic scans is greater than 3 months. No PD is observed on the latest scan before the gap occurs.	0	The date of the latest tumor assessment before the gap– the date of starting treatment
No disease progression per RECIST 1.1 is observed on the post-treatment scans and patient dies before the next scheduled scan + 1 month.	1	The date of death – the date of starting treatment
No disease progression per RECIST 1.1 is observed on the post-treatment scans and patient dies. The period from the latest scan to death is greater than 3 months.	0	The date of the latest tumor assessment – the date of starting treatment
No post-treatment scan is available and patient dies before the first scheduled scan + 1 month.	1	The date of death – the date of starting treatment
No post-treatment scan is available and patient is lost follow up or patient dies >3 months later after starting treatment.	0	0

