Electrocardiogram (ECG) ¹¹	Х										

						cycle ** = 28 days)			Maintenance Phase		
Procedure	Baseline ¹	Lead-In Day -14*	Lead-In Day -7	Day 1 (±3 days)	Day 8 (±1 day)	Day 15 (±3 days)	Day 22 (±1 days)	Week 6 (+14 days)	Every 4 weeks, Beginning on week 16***	Every 8 weeks (±7 days) ²	EOT ³ 28 days After Last Dose (±7 days)
Urinalysis ¹²	X										
Pregnancy test/ Assessment WOCBP ¹³	х	X*		X					X		
Tumor Assessments Imaging ¹⁴	Х									X	X ²⁰
CA19-9		X*								x	X ²⁰
Entinostat ¹⁵		x	X	Х	X	Х	х	х	Х		
Nivolumab ¹⁶				х		х		х	Х		
Peripheral blood for PBMC (up to 180cc) ¹⁷		X		х				Х			Х
Peripheral blood for plasma (up to 20cc) ¹⁷		х		х				Х			Х
Serum (up to 10cc) ¹⁷		Х		Х				X			Х
Fresh Tumor Biopsy ¹⁸		х		X ¹⁸				X ¹⁹			X ²⁰
Archival Tumor Sample ²¹	X										
Concomitant Medication Review	X	X		X		X		X	X		X
Symptom/Toxicity Assessment ²²			X	Х		X		X	X ²²		Х

						cycle ** = 28 days)			Maintenance Phase		
Procedure	Baseline ¹	Lead-In Day -14*	Lead-In Day -7	Day 1 (±3 days)	Day 8 (±1 day)	Day 15 (±3 days)	Day 22 (±1 days)	Week 6 (+14 days)	Every 4 weeks, Beginning on week 16***	Every 8 weeks (±7 days) ²	EOT ³ 28 days After Last Dose (±7 days)
Follow-up/Survival ²³											X ²⁴

Study Calendar: Entinostat and Nivolumab

- Baseline evaluations should occur within 28 days prior to registration, unless otherwise noted. NOTE: No window applies to demographics, informed consent, or height at baseline. If any assessments are repeated after registration and prior to dosing on Day -14, subjects must maintain eligibility requirements in order to initiate therapy. Biopsies should be performed only after patient is deemed eligible and registered on the trial.
- ² Disease assessments will be conducted every 8 weeks (+/- 1 week) from Cycle 1 Day1 for the first 6 months; this timeframe may then be extended to every 12 weeks (+/- 1 week) at the discretion of the treating provider.
- ³ A mandatory End of treatment (EOT) visit should be performed 28 days (± 7 days) after the last dose of entinostat to determine patients' safety outcome. Repeat any physical or laboratory assessments after the last dose of any study treatment if last assessment >7 days prior.
- ^{4.} Complete physical exam will be completed at baseline; focused physical examinations may be conducted thereafter.
- ^{5.} Hematology Panel includes at a minimum: basophils, eosinophils, hematocrit, hemoglobin, lymphocytes, monocytes, neutrophils, platelet count, and total white cell count.

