12.3.2 Analysis of Secondary Endpoints

- OS is defined as the duration of time from start of study treatment to time of death. For subjects lost to follow-up or whose vital status is unknown, every effort will be made to determine the date such subjects were last known to be alive. Such efforts may include phone calls, certified mail, and the checking of public records. Subjects who are alive or lost to follow-up as of the data analysis cutoff date will be right-censored. The censoring date will be determined from the date the subject was last known to be alive.
- PFS is defined as the time from cycle 1, day 1 of immunotherapy until first documented local progression or death due to any cause. Disease progression will be assessed using RECIST (version 1.1). Due to the expectation that some patients may experience delayed clinical responses to therapy, patients with disease progression by radiographic imaging or laboratory parameters during a 12-week evaluation period but without rapid clinical deterioration or significant change in performance status that requires additional immediate therapy may continue to receive treatment on study.

Subjects that meet the above criteria and continue on study therapy must discontinue treatment upon documentation of disease progression on the second scan. The date of progression will be backdated to the time of first RECIST criteria progression. Tumor assessments will be made using RECIST 1.1 and immune-related response criteria (irRC). Individuals will be censored at the date of the last scan for PFS if no event occurs.

Median time to event will be calculated and reported with confidence intervals.

Analysis of PFS will be restricted to evaluable individuals who complete at least one dose of entinostat, while the analysis of OS will be performed on all evaluable patients.

OS curves, OS medians with 95% CIs, and OS rates at 6, 12, 24 and 36 months with 95% CIs will be estimated using Kaplan-Meier methodology

PFS curves, PFS medians with 95% CIs, and PFS rates at 6, 12 and 24 months with 95% CIs will be estimated using Kaplan-Meier methodology.

• Duration of response (DOR) will be calculated for subjects who achieve a best overall response of CR or PR with entinostat in combination with nivolumab. For such subjects,

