duration of response is defined as the number of weeks from the start date of PR or CR (whichever response is recorded first) and subsequently confirmed to the first date that recurrent or progressive disease or death is documented. In such cases, recurrent or progressive disease will be assessed relative to the smallest tumor measurements recorded since the start of study treatment. The primary analysis of duration of response will be based on the time point responses, best overall response, and PD status that are determined by the review of the investigator

DOR will be summarized descriptively using the Kaplan-Meier method with 95% confidence intervals (CIs)

• The safety analysis will be performed in all subjects who receive any amount of study drug. A baseline measurement and at least 1 laboratory or other safety-related measurement obtained after at least 1 dose of study treatment may be required for inclusion in the analysis of a specific safety parameter (e.g., lab shifts from baseline).

A complete list of all AE data will be provided along with an assessment of NCI CTCAE grade and relationship to study drug. The incidence of AEs will be tabulated by subgroups of interest (e.g. grade 3 or higher, organ class, relationship to study drug).

For analyses at the individual level, the highest grade and relationship to study drug will be assumed if multiple events have occurred.

Toxicity will be tabulated by type and grade and will be summarized with descriptive statistics. Other safety data will be assessed in terms of physical examination, clinical chemistry, hematology, vital signs, and ECGs. Negative binomial regression and Cox proportional hazards models will be used to assess the rate of AE and time to first toxicity, respectively.

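### Duration of response is censored at the start of new therapy, although PFS, and responders without new therapy, are censored at the last tumour assessment

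*Combined protocol and SAP*

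**What the plan says.** Section 8.3.5 has two censoring rules for DOR. For patients with neither progression nor new therapy: "Subjects who remain alive and have not progressed or received new therapy will be censored on the date of last protocol specified tumor assessment". For the others: "Subjects who receive new therapy will be censored at the start of the therapy". Both rules are repeated for duration of stable disease.

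Section 8.3.6 treats the same situation differently for PFS. A patient who begins alternate therapy before progressing "will be censored at the time on the date of the latest tumor assessment before starting the alternate therapy". It adds: "Only radiographic scans used to tumor assessment per RECIST 1.1 before starting the alternate therapy will be counted".

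Section 12.3.2 is consistent with 8.3.6 on PFS: "Individuals will be censored at the date of the last scan for PFS if no event occurs". For DOR it gives the starting point ("duration of response is defined as the number of weeks from the start date of PR or CR"), the event (recurrence, progression or death) and the Kaplan-Meier method, but no censoring rule. The rule in 8.3.5 is therefore the one that applies.

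On scan timing, the Study Calendar in Section 10 states: "Disease assessments will be conducted every 8 weeks (+/- 1 week) from Cycle 1 Day1 for the first 6 months". After that the treating provider may extend the interval to 12 weeks, again with a one-week window.

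**The concern.** Response status is known only up to the last scan. Censoring at the start of new therapy treats the time from that scan to the new therapy as observed, progression-free follow-up. The patient stays in the Kaplan-Meier risk set during that time without having been assessed.

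There are two inconsistencies. Within 8.3.5, a responder who switches therapy is credited beyond the last scan, while one who does not switch is not. Between 8.3.5 and 8.3.6, DOR and PFS for the same responder end on different dates, although both rest on the same RECIST progression data. What is at stake is the reported DOR curve and median, which will rest on a handful of responders per cohort.

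**Working it through.** The plan states no figure for DOR or its censoring, so there is none to reproduce. Its design figure does reproduce: the probability of stopping at stage 1 with a 5% ORR is 0.95^13 = 0.513, against the stated 51%. Nothing below changes the design.

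**1. Length of the unassessed gap.** Inputs: 8-week and 12-week intervals, each scan with a window of ±1 week (Section 10). The longest gap has the last scan one week early and new therapy starting just before a next scan that is one week late.
- 8-week schedule: 8 + 1 + 1 = 10 weeks
- 12-week schedule: 12 + 1 + 1 = 14 weeks

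A missed scan makes either gap longer.

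**2. Number of responders.** Inputs: 27 evaluable patients per cohort, null ORR 5%, alternative 20% (Section 12.2).
- At 20%: 27 × 0.20 = 5.4
- At 5%: 27 × 0.05 = 1.35

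**3. Direction.** At each event time the Kaplan-Meier curve is multiplied by 1 − d/n, where d is the number of events and n the number at risk. Moving a censoring date later raises n by one at every event time inside the gap and leaves d unchanged. The curve can stay the same or rise; it cannot fall. If no other responder has an event in the gap, the curve is identical.

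**4. Small example.** Three responders, with events at weeks 16 and 32 and the third patient censored.
- Censored at week 8 (last scan): at week 16, n = 2 and S = 1/2, so the median is 16 weeks.
- Censored at week 17 (new therapy): at week 16, n = 3 and S = 2/3; at week 32, n = 1 and S = 0, so the median is 32 weeks.

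**5. Simulation.** These assumptions are not in the documents: 5 responders; exponential DOR with true median 26 weeks; 10% or 30% of responders starting new therapy before true progression, independently of it; scans at weeks 8 and 16 of response and every 12 weeks after that, each moved by up to one week; the last scan before the switch missed with probability 0, 0.5 or 1. Progression is dated at the scan that detects it. Response confirmation is not modelled. There were 3,000 simulated trials per row.

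| Switching | P(last scan missed) | 26-week DOR, censored at new therapy | 26-week DOR, censored at last scan | Difference | Trials in which medians differ | Mean gap (weeks) |
|---|---|---|---|---|---|---|
| 10% | 0 | 0.650 | 0.644 | 0.006 | 4.0% | 5.4 |
| 10% | 0.5 | 0.661 | 0.652 | 0.009 | 8.2% | 10.0 |
| 10% | 1 | 0.658 | 0.644 | 0.014 | 12.6% | 13.8 |
| 30% | 0 | 0.655 | 0.639 | 0.016 | 8.2% | 5.2 |
| 30% | 0.5 | 0.668 | 0.635 | 0.033 | 17.8% | 9.3 |
| 30% | 1 | 0.680 | 0.629 | 0.051 | 26.0% | 13.2 |

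With perfectly regular 8-weekly scans and none missed (true medians of 24 and 36 weeks tried), the two rules gave identical medians and 24-week estimates. All detected progressions then fall on the same 8-week grid, and none lies between a scan and a switch that precedes the next scan.

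**The case against.** The strongest reply is that this is a choice and not an error. DOR and PFS are separate endpoints, 8.3.5 is complete and can be programmed as written, and 12.3.2 states nothing that competes with it. That stands as far as it goes. A reader might infer from the silence of 12.3.2 that the DOR rule is undefined, but it is not. The reply does not explain why 8.3.5 uses the last assessment for one group of responders and a later date for the other.

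A reader might also infer that new therapy is often prompted by worsening that was never recorded, so that the bias is substantial. The documents give no frequency. They foresee the pathway: Section 8.3.3 has a reporting category for clinical deterioration without objective progression, and Section 4.8 lists the need for other anticancer drugs as a reason to stop treatment. They also contain partial safeguards. Section 8.3.3 asks that progression still be documented after treatment stops. The calendar marks tumour imaging at the end-of-treatment visit and requires restaging near 6 months for patients who stop earlier. Disease status after stopping for reasons other than progression is collected until progression where possible. These steps shorten the gap but do not close it.

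Finally, a reader might infer that DOR will be lengthened. A censored patient adds no event, so the estimate moves only under the condition in step 3 of the working. With no missed scans the average simulated shift was 0.006 to 0.016. The largest shift, 0.051, needs 30% switching and every last scan missed.

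**Conclusion.** The inconsistency is real and no other section removes it. The rule can leave the DOR curve unchanged or make it too high; it cannot make it too low. In most plausible settings the effect is small: at most about 0.05 on the 26-week estimate under the assumptions tried, with the median affected in 4% to 26% of simulated trials that had five responders. If switching is driven by worsening, which is an assumption, the bias would probably be larger, because the simulation took switching as independent of progression.

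Only responders who start new therapy before documented progression are affected (and, for duration of stable disease, patients with stable disease who do so). The figure of about five responders holds only near a 20% ORR. The documents do not support any reading that carries this through to the primary conclusion: the response count, the stop at 0 of 13, the requirement of 4 or more of 27, and the sample size do not use DOR. This is a low-priority but worthwhile correction.

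**What to change.** In Section 8.3.5, replace the new-therapy sentence for both DOR and duration of stable disease with a rule such as: *patients who start new anticancer therapy before documented progression or death are censored at the date of the last tumour assessment before that therapy starts*. This matches 8.3.6. State the same rule under DOR in Section 12.3.2, so that the statistical section can be read alone.

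The cost is a sentence in each place. No new data, visits or patients are needed. The only downside is that reported DOR may be slightly shorter.
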